# 7.2. Statistical Analysis

Data will be analyzed using intent-to-treat methodology (Herman et al JBJS 2009), utilizing the original treatment group to which a patient was assigned. Differences between means will be analyzed using Student's t-test, while categorical variables will be tested using frequency tabulations comparing outcomes between treatments with the Pearson chi-square test. Differences will be considered significant at the level of  $p \le 0.05$ .

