#### 1.3 Outcome Assessments

These three groups will be analyzed using several outcome measures including validated patient-reported outcome measures the Knee Injury and Osteoarthritis Outcome Score(KOOS) [1], and Veterans RAND 12 item health survey (VR-12))[2], knee active range of motion (extension, flexion), quadriceps femoris muscle (QFM) strength, the Timed Up and Go Test [3] and the Stair Climb Test. The primary endpoint for the study is QFM strength. However, of secondary interest will be: 1) other physical performance measures (i.e. limb symmetry index and gait speed, activity levels), 2) Visual Analogue Scale (VAS) pain levels [4], on outpatient follow-up and immediately before & after NMES therapy, 3) length of stay, 4) Patient dependence on assistive device, 5) Patient satisfaction measures, 6) Patient discharge disposition, 7) Patient readmission rate. The proprietary app for this product will be used to track device usage (intensity, duration of session, frequency of use), knee range of motion and gait speed.

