### 5.2. Exclusion Criteria

- 1. BMI > 40
- 2. Inflammatory arthritis
- 3. Patients who are expected to be in extended care facilities after surgery
- 4. Patients who have used an at-home NMES device in the past
- 5. Preoperative daily use of narcotics (i.e., high tolerance)
- 6. Already enrolled in another research study, including the present study for contralateral knee
- 7. Other lower-extremity orthopaedic conditions which could interfere with limb function, especially those with significant pain requiring daily analgesic intake
- 8. Patients with concurrent abdominal, inguinal or femoral hernias
- 9. Cutaneous lesions in areas of electrode pad placement

- 10. Patients with a history of epilepsy
- 11. Patients with a cardiac pacemaker/defibrillator
- 12. Allergy to adhesives
- 13. Inability to meet follow-up visits required for the study
- 14. Patients who are a risk for poor compliance or have a poor understanding of the use of the NMES device
- 15. Condition deemed by physician or medical staff to be non-conducive to patient's ability to complete the study, or a potential risk to the patient's health and well-being

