#### Preoperative Care

At 4 weeks  $\pm$  7 days prior to scheduled date of surgery, a randomization envelope will be opened indicating whether the patient is randomized into the combined treatment group, postoperative NMES only group, or the standard-of-care group. (See section 4 for more detail). Patients randomized to the combined treatment group will begin using the NMES device immediately until the day of surgery. Patients will be thoroughly educated on the use of the device at the time the patient receives the device. Patients may be given the device and educated by either physical therapists and or brace fitting specialists who are participating in the study. In addition, the study sponsor, Cymedica Orthopaedics will be available to provide technical support for the patient at any time if a device malfunction occurs. The study sponsor will not collect any information regarding the patient's status in the study, and will only know that the patient has a device but not which group they are in and or what phase of treatment is occurring. Patients will be asked to use the NMES device at the highest tolerable intensity. At the beginning of the study, all patients will be given an activity monitoring device made by Misfit Wearables®, which is similar to a Fitbit bracelet that they will wear daily. Activity levels will be uploaded and incorporated into online app. We will monitor for any changes in activity/ambulation among the groups to determine the effect of NMES usage on activity.

To ensure the validity of the NMES devices ability to achieve and deliver therapeutic doses in the NMES trial, the NMES device will be set at an intensity that has at least a minimal

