# Postoperative Care

Postoperative care will be standardized according to the protocol routinely used at our institution with rapid mobilization, gait training and range of motion [11]. Outpatient physical therapy will be scheduled as needed based on the therapist's assessment of recovery. Physical therapy locations must be Cleveland Clinic affiliated due to the need to use staff who have appropriate training on the NMES device usage to ensure accurate data collection. Pain will be controlled with orally administered long- and short-acting narcotics supplemented by parenteral narcotics as necessary. All study patients will receive standard of care anesthesia protocol.

Following discharge, patients will return for visits with a member of the research team at 3 weeks  $\pm$  7 days, 6 weeks  $\pm$  7 days, 12 weeks  $\pm$  7 days. Data will be collected and reported on the appropriate Case Report Forms at these follow-up visits.

As a last resort, if a patient is unable to keep one of these appointments, he/she will be either be mailed or emailed the OrthoMidas forms so the patient can fill them out. The patient will date and time the forms. They will then send the form back in a pre-addressed envelope. The patients email will be verified by the patient during a clinical visit to ensure accuracy of the correct recipient. Patients not responding to the initial mailer will be contacted by phone and forms may be administered over the phone. The mailers and/or phone calls will allow us to collect all data except the physical function measures. At the completion of the study, patients

will be given a voluntary survey about their experience with the clinical trial, which will be given in person, and or mail and email.

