# **Pretreatment Assessments**

Before treatment, the following assessments/tests will be performed and the results will be recorded on the appropriate pages of the CRF, and or Microsoft excel, Microsoft Word, and REDCap:

- Eligibility criteria, including written informed consent
- Age, gender, height/weight/BMI
- Concomitant diseases
- Physical examination
- Baseline range of motion of affected knee
- Baseline timed up and go test (TUG test, detailed in Appendix A and as described by Podsiadlo et al.)

- Baseline Stair Climb test
- Baseline QFM strength
- Baseline Modified KOOS and VR-12 assessments
- Baseline VAS pain score
- Current medications
- Any use of ambulation assist device

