# **Presurgery Assessments**

Before surgery, the following assessments/tests will be performed and the results will be recorded on the appropriate pages of the CRF, and or Microsoft excel, Microsoft Word, and REDCap:

- Device usage patterns (thru app for preop NMES group)
- Range of motion of affected knee
- TUG test
- Stair Climb test
- QFM strength
- Modified KOOS and VR-12 assessments
- VAS pain score
- Current medications
- Activity levels using Misfit Wearables® fitness monitor will be uploaded and incorporated into online app

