### 7. CLINICAL OUTCOMES

# 7.1. Sample Size Justification

A recent review paper written by Maddocks et al looked at eight different studies that used quadriceps muscle strength as an outcome and created a pooled analysis. They found a standardized mean difference of 0.90 for quadriceps muscle strength between control and NMES intervention groups. Sample size was calculated using this standardized mean difference, along with 80% power and the level of significance (p-value) set to 0.05. This study will require 20 patients per group. However, adding in a 10% expected dropout rate, planned enrollment will be 22 patients per group for a total enrollment of 66 patients.

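### The primary strength analysis is an unadjusted t-test with no named visit, although a pretreatment strength value is already scheduled and adjusting for it costs almost nothing

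*Combined protocol and SAP*

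**What the plan says.** Section 7.2 is the whole analysis plan: intent-to-treat, the Pearson chi-square test for categorical variables, a 0.05 threshold, and for means "Differences between means will be analyzed using Student's t-test". It names no covariate, no visit, no repeated-measures model, no rule on raw value versus change, and no rule for missing values.

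Section 1.3 states "The primary endpoint for the study is QFM strength" and attaches no time point. Section 7.1 does not tie its standardized difference of 0.90 to a visit either, and does not say whether that figure is on the SD of raw values or of changes. It concludes "This study will require 20 patients per group".

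The table in section 1.4 schedules strength five times: week -4, around surgery, and weeks 3, 6 and 12. The pretreatment list in section 6.3 includes "Baseline QFM strength", and the presurgery list repeats the strength test. Between those two tests, section 6.2 (Preoperative Care) says "Patients randomized to the combined treatment group will begin using the NMES device immediately until the day of surgery".

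For missed visits, section 6.2 (Postoperative Care) offers mail and telephone contact, which "will allow us to collect all data except the physical function measures".

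**The concern.** There are two separate problems.

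The first is specification. Three postoperative visits, each analysed as a raw value or as a change, could all be presented as the primary result. The plan does not prevent that choice from being made after the data are seen.

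The second is efficiency. The trial is small, and a patient's strength before treatment may well predict strength afterwards. A t-test on follow-up values discards that information. A t-test on changes uses it badly when the correlation is low. A strength test that is missed cannot be recovered by mail or telephone, so a single-visit t-test simply loses that patient.

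**Working it through.** **Inputs.** From section 7.1: difference 0.90 SD, alpha 0.05, 80% power, 20 analysable per arm, 22 enrolled per arm. From section 5.4: three arms, 1:1:1. Assumed, because the documents are silent: two-sided testing, baseline-to-follow-up correlation ρ, and equal SDs at both times.

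**The plan's own figure.** n = 2 × ((1.960 + 0.842)/0.90)² = 19.4, rounded up to 20 per arm. This reproduces the plan. By the noncentral t distribution, 20 per arm gives 79.2% power.

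**Power for one pairwise contrast.** All rows use the noncentral t with noncentrality (0.90/s) × √(20/2), where s is the SD that applies:

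- raw-value t-test: s = 1, 38 df
- change-score t-test: s = √(2(1−ρ)), 38 df
- three-arm ANCOVA: s = √((1−ρ²)(1 + 1/55)), 56 df. The factor 1 + 1/(3n−5) allows for chance baseline imbalance.

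| ρ | Raw t | Change t | Three-arm ANCOVA | Gain over better t-test (points) |
|---|---|---|---|---|
| 0.3 | 79.2% | 65.0% | 82.8% | 3.6 |
| 0.5 | 79.2% | 79.2% | 89.3% | 10.1 |
| 0.7 | 79.2% | 94.7% | 97.3% | 2.5 |
| 0.8 | 79.2% | 99.2% | 99.6% | 0.4 |

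Simulation of the ANCOVA (100,000 runs) gave 82.7, 89.1, 97.2 and 99.6%.

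**If 0.90 is on the change SD.** The raw difference becomes 0.90 × √(2(1−ρ)):

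| ρ | Raw t | Change t | Three-arm ANCOVA |
|---|---|---|---|
| 0.3 | 90.7% | 79.2% | 93.0% |
| 0.5 | 79.2% | 79.2% | 89.3% |
| 0.7 | 57.5% | 79.2% | 85.2% |
| 0.8 | 41.9% | 79.2% | 83.2% |

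ANCOVA is the best of the three in every row of both tables.

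**Cost if the baseline is useless (ρ = 0, raw SD).** Three-arm ANCOVA has 79.16% against 79.20% for the planned t-test. Two changes cancel here: pooling the variance over three arms raises power to 79.9%, and the covariate then takes back about 0.7 points. In a two-arm model, without that pooling, the covariate costs about 1.2 points (79.2% to 78.0%).

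**Open choice of visit.** If one arm contrast is tested at 3, 6 and 12 weeks, each at 0.05, and any visit could be claimed, the false-positive chance by simulation (200,000 runs) is 12.5, 11.1, 9.9 and 8.4% at between-visit correlations of 0.5, 0.7, 0.8 and 0.9. For independent visits it would be 1 − 0.95³ = 14.3%.

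**Missed strength tests.** Suppose 2 of 22 per arm miss only the primary-visit test. With baseline correlation 0.5 and between-visit correlation r, the partial correlation given baseline is c = (r − 0.25)/0.75, and the other two visits explain R² = 2c²/(1 + c) of the remaining variance. A mixed model then has effective n = 1/[(1 − R²)/20 + R²/22]. At r = 0.5, R² = 0.167 and n = 20.3. At r = 0.9, R² = 0.805 and n = 21.6. It recovers 0.3 to 1.6 patients per arm, and nothing for a patient with no postoperative test.

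**The case against.** The strongest reply is that the efficiency part is a preference. The t-test is valid, and the plan's own sizing reaches 79.2% without adjustment, close to its 80% target. The gain depends on three things the documents do not give: the correlation, the ratio of SDs before and after surgery, and the SD behind 0.90. That stands, and the gain must be stated as conditional.

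The near-zero cost also mixes two changes. Like for like, the covariate costs 0.7 points in three arms or 1.2 in two, and a two-arm ANCOVA gains 2.5, 9.2, 2.2 and 0.3 points over the better t-test at the four correlations, slightly less than the table shows. That stands too, but the cost remains small and the direction does not change.

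Missed tests may be few: section 5.2 excludes patients with "Inability to meet follow-up visits required for the study", section 8 pays for visits, and section 7.1 allows 10% dropout. These measures limit the loss but are not an analysis rule. The mixed-model benefit is modest in any case.

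Naming a visit does not settle multiplicity across arms. Three pairwise contrasts at one visit still carry about a 12% chance of at least one false positive. That is a separate point, and this fix does not claim to solve it.

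Finally, is the week -4 value always available? Section 5.3 lets telephone-recruited patients complete consent just before surgery, while section 6.2 puts randomization and device set-up at week -4. Section 5.3 does not itself move the strength test, but the pretreatment list in 6.3 includes consent, so the two sections must be reconciled. Nor does any section place the strength test before the envelope is opened.

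**Conclusion.** The point holds. It is a gap in the analysis specification and a missed improvement that needs no new data; the sample size and the validity of the t-test are not in question. The open visit and outcome form matter whatever the baseline correlation: 8 to 13% false positives for one contrast over three visits, assuming between-visit correlations of 0.9 down to 0.5. The precision gain over the better t-test is 0.4 to 10.1 points for correlations of 0.3 to 0.8 on the raw-SD reading. The stronger argument is robustness. The sponsor does not know the correlation or which SD the 0.90 refers to, and a wrong choice between the two t-tests can be expensive (41.9% against 83.2% at worst in the tables). ANCOVA avoids having to guess. Confidence in the size of the gain is moderate, because it rests on assumed correlations, equal SDs and a common residual variance across arms.

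**What to change.** Amend section 7.2 before outcome data are seen:

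1. Name one primary postoperative visit for QFM strength (3, 6 or 12 weeks).
2. Analyse strength in one three-arm model adjusted for the week -4 pretreatment value, and take the pairwise contrasts from it. Choose one of two forms and write it down: ANCOVA at the named visit, or a mixed model over weeks 3, 6 and 12 that also uses the other visits of patients who miss one. State the missing-data assumption.
3. State that the presurgery value is not the covariate. It follows NMES use in the combined arm, so adjusting for it could remove part of the treatment effect.
4. Keep randomized patients who lack a week -4 value, either by simple baseline imputation or by modelling baseline as an outcome. Fix which.

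Alongside this, reconcile sections 5.3 and 6.2 on timing, and state that the baseline strength test precedes opening of the envelope.

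The cost is wording: no new visits, tests or patients. If the correlation were zero, power would fall by less than 0.1 point against the planned t-test (0.7 points against an unadjusted three-arm contrast). The model assumes a common residual variance across arms.

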### 2. BACKGROUND

The current standard for rehabilitation after TKA consists of guided exercise therapy for up to 12 weeks after surgery. This includes inpatient, home, and outpatient therapy. The surgery and rehabilitation are highly successful at reducing or eliminating pain experienced preoperatively. However, QFM strength, overall function, and knee range of motion are often worse than preoperative levels for as long as 6 months after surgery and in some cases may persist for many years after that. Such quadriceps strength impairments after TKA have been largely attributed to voluntary activation deficits and can lead to a decrease in functional performance such as decreased gait speed, decreased balance which can lead to falls, and decreased stair climbing & chair rise abilities [5,6]

Since therapy alone does not adequately restore or improve upon the preoperative functional capabilities in a consistent and timely manner, it has been suggested that NMES used adjunctively with postoperative rehabilitation will alleviate the quadriceps muscle activation deficits. Early NMES use after TKA has been shown to: reduce knee extensor lag [7], increase walking speed [8], and improve QFM strength, knee range of motion, and function [5]. However, NMES initiated one month after TKA did not lead to improved QFM strength or function beyond the standard benefits gained from exercise alone [9], thus suggesting that the timing of NMES application after TKA is important.

It has previously been shown that preoperative QFM strength is predictive of postoperative function [10] but the benefit of prehabilitation remains in question [11–13]. To date, there has only been one pilot study assessing the benefits of NMES when initiated preoperatively[14]. This study only included 14 patients (9 NMES, 5 control) but was able to show that preoperative NMES usage may lead to greater QFM strength gains after TKA. Therefore, it will be important to assess the benefits of NMES both preoperatively and postoperatively in order to determine how it will be most beneficial to TKA patients.

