#### **Postoperative Assessments**

After surgery, one or more of the following will be collected through the online app and at follow-up visits.

- Device usage patterns (thru app)
- Range of motion of affected knee (thru app and at follow-up)
- TUG test
- Stair Climb test
- QFM strength
- Modified KOOS and VR-12 assessments
- VAS pain score

- Length of stay (hospital, extended care facility)
- 90 day readmission rate
- Discharge Disposition (home vs skilled nursing facility vs inpatient rehabilitation)
- Patient Satisfaction measures
- Any use of an ambulation assist aid
- Activity levels using Misfit Wearables® fitness monitor will be uploaded and incorporated into online app

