### Procedure

- 1. Subject wears his regular footwear and uses his customary walking aid.
- 2. No physical assistance is provided.
- 3. Subject starts with his back against the chair, his arms resting on the chair's arms, and his walking aid at hand.
- 4. Instruct subject that, on the word 'go', to get up and walk at a comfortable and safe pace to the line on the floor, turn, return to the chair, and sit down again.
- 5. Allow subject to practice the test once before being timed to become familiar with the test.

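### The plan gives no analysis value to a patient who attends but cannot complete the TUG or Stair Climb test, so a t-test on times compares only those able and is biased if inability differs by arm

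*Combined protocol and SAP*

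**What the plan says.** Section 1.3 lists "the Timed Up and Go Test [3] and the Stair Climb Test" among the outcome measures, and Specific Aim 1 concerns physical performance. They are not the primary endpoint: "The primary endpoint for the study is QFM strength".

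Section 7.2 states "Data will be analyzed using intent-to-treat methodology", with patients kept in their assigned group. It then names two methods: "Differences between means will be analyzed using Student's t-test", and a Pearson chi-square test for categorical variables. It has no rule for missing data or for a test that was attempted and not completed.

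Appendix A describes TUG as a timed test. "Subject wears his regular footwear and uses his customary walking aid", the chair has arms, and "No physical assistance is provided". It gives no maximum time and no assigned value for a patient who cannot finish.

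Section 6.3 lists "Stair Climb test" under the pretreatment, presurgery and postoperative assessments. The protocol describes no procedure for it, and the schedule in section 1.4 omits it. TUG is scheduled at 3 weeks ± 7 days, which is as early as day 14.

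**The concern.** A mean time needs a time from every patient. Someone who comes to the visit and cannot rise, walk the course or climb the stairs has none, yet that failure is itself the result of the test. Assigning patients to their original group, as intent-to-treat requires, does not supply the absent number. With no rule, the t-test compares those able in one arm with those able in the other. Randomisation does not protect that comparison, because ability is measured after treatment and may depend on it.

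At stake is the Aim 1 comparison on the timed tests at the early postoperative visits. The groups are small: at 20 evaluable patients per arm, two to four patients without a time are 10-20% of an arm. The Postoperative Care text in section 6.2 adds a second source of blanks, because contact by mail or phone after a missed visit cannot recover physical function measures. Unless the reason is recorded on the day, the two kinds of blank cannot be told apart later.

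**Working it through.** **The plan's own figure.** Section 7.1 uses a standardised difference of 0.90, 80% power and a 0.05 level. The two-sided normal formula gives n = 2(1.960 + 0.842)² / 0.90² = 19.4, so 20 per group, as stated. The t-based figure is 20.4, and power at exactly 20 per group is 79%. This sizing is for quadriceps strength. The documents give no SD, effect or inability rate for TUG or Stair Climb, so everything below rests on assumptions.

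**Model.** Let standardised log-time be N(0, 1) in controls and N(−d, 1) with NMES, where higher is slower. A patient beyond a fixed cutoff c has no time. If a share p of controls is unable, c = Φ⁻¹(1 − p). The mean among those able, in an arm with mean μ, is μ − φ(c − μ)/Φ(c − μ). The observed benefit is the control mean minus the NMES mean.

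**Worked case, p = 20%, d = 0.90.**
- c = 0.842.
- Controls: 0 − 0.280/0.800 = −0.350.
- NMES: −0.90 − 0.0875/0.9592 = −0.991.
- Observed benefit: 0.991 − 0.350 = 0.641 SD, which is 71% of 0.90.

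**Range, 20 per arm, two-sided 0.05.** Power is by simulation (6,000 runs or more). Where two values are shown, the lower is a t-test on seconds, taking time = exp(0.4 × latent value), and the upper is a t-test on log-time. The 0.4 is an assumption.

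| Controls unable | NMES unable (d = 0.90) | 0.90 SD appears as | Retained | t-test power | 0.50 SD appears as |
|---|---|---|---|---|---|
| 2% | 0.2% | 0.86 | 95% | 74-77% | 0.47 |
| 5% | 0.5% | 0.81 | 90% | 72-74% | 0.43 |
| 10% | 1.5% | 0.74 | 82% | 67-68% | 0.39 |
| 20% | 4.1% | 0.64 | 71% | 57-59% | 0.33 |
| 30% | 7.7% | 0.56 | 62% | 48% | 0.28 |

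With nobody unable, t-test power at 0.90 SD is 79% on log-time and 76% on seconds. A rank test with unable patients placed last has about 77% in every row.

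**Does the direction always run this way?** No.
- *Equal shares unable under a pure shift.* Each arm loses the same upper fraction, both means move by the same amount, and there is no bias.
- *More slow NMES patients without times.* Take 15% of NMES patients and 5% of controls missing from the slow end, with a true benefit of 0.30 SD. The mean displacements are −0.274 and −0.109. The observed benefit is −0.109 − (−0.274 − 0.300) = 0.466 SD, which is too large.
- *NMES only makes half of the otherwise unable patients barely able and speeds up nobody else.* At 5/10/20/30% of controls unable, the observed benefit is −0.04/−0.08/−0.13/−0.18 SD, which has the wrong sign. Significant apparent harm occurs in 5%, 7% and 10% of simulated trials at 10%, 20% and 30% unable.

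**The case against.** The strongest reply is that inability may be rare. For TUG, the walking aid and the arm chair help a weak patient to finish. Section 5.2 excludes patients expected to need extended care and those with other interfering lower-limb conditions, and section 6.2 describes rapid mobilisation and gait training. These points stand. They make 10-30% doubtful for TUG, and at 2% the loss is small. The background remark about "decreased stair climbing & chair rise abilities" describes reduced performance and is not evidence that patients cannot complete a test.

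Inability is easier to imagine on stairs. However, section 1.4 gives no visit for that test, and the postoperative list in 6.3 says only that one or more of its items will be collected. That Stair Climb is done at day 14 is therefore an inference.

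A reader might infer that the plan drops unable patients. It does not say so; it is silent. Its chi-square test could compare able with unable, and use of ambulation aids is recorded at every visit. But neither is assigned to this purpose, and a t-test on times has nothing else to use.

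A reader might also infer that a benefit of NMES will certainly be understated, or will look like harm. The documents do not support either. The direction depends on which arm has more unable patients. The reversal in expectation appeared only when benefit was confined to patients near the cutoff; at 20% unable, a uniform gain of about 0.18 SD among the other patients would cancel it.

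Finally, deciding between unable and other reasons calls for judgement, and no assessor blinding is described. That is a fair caution about the remedy.

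**Conclusion.** The point holds in conditional form. Section 7.2 offers only a t-test on means for the timed tests, and nothing in the plan gives a value to a patient who attends and cannot complete one. The comparison is thus restricted to those able. It is biased if inability differs by arm: towards understating benefit if NMES reduces inability, and towards overstating it if more slow NMES patients lack times.

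The size is unknown because no inability rate is given. If the benefit is a uniform 0.90 SD shift (a figure borrowed from the strength calculation) with a sharp cutoff, between 90% and 62% of it remains visible as the share of controls unable goes from 5% to 30%. Power falls from about 72-74% to 48%. At 2% or fewer unable the matter is minor.

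The primary strength analysis is untouched. This is a worthwhile change to the analysis of secondary performance measures, and it does not threaten the trial's main conclusion.

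**What to change.** 1. On the CRF, for each timed test, record unable to complete separately from not done for other reasons, with a short written definition applied alike in all arms.
2. In section 7.2, compare TUG and Stair Climb times by a rank test with unable patients given the worst rank. For TUG, an alternative is speed (6 m out and back, divided by time) with unable set to 0. Tests not done for other reasons stay missing and are not ranked worst.
3. Report the share unable by arm and visit.
4. Add Stair Climb to the schedule in section 1.4 so that its visits are clear.

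The cost is one CRF item, a sentence or two in 7.2 and one schedule row. The test result becomes a rank or a speed in place of seconds; times among those able can still be shown descriptively. With nobody unable, the rank test gives up about 2 percentage points of power against a t-test on log-time (77% against 79%). It also does not create power where only a few patients move from unable to barely able: in that scenario it detected benefit in about 3-4% of simulated trials. It does, however, rank those patients above the ones still unable, which the t-test on available times cannot do.

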#### 1.4 Time and Events Schedule

|                              | Preop                                  | Day of Surgery | 3 weeks    | 6 weeks    | 12 weeks  |
|------------------------------|--|----------------|------------|------------|-----------|
|                              | $(4 \text{ weeks} \pm 7 \text{ days})$ | (- 7 days)     | (± 7 days) | (± 7 days) | (± 7days) |
|                              | prior to surgery)                      |                |            |            |           |
| Outcome Scores               | X                                      | X              | X          | X          | X         |
| Range of Motion              | X                                      | X              | X          | X          | X         |
| QFM strength                 | X                                      | X              | X          | X          | X         |
| TUG Test                     | X                                      | X              | X          | X          | X         |
| VAS Pain                     | X                                      | X              | X          | X          | X         |
| Narcotic usage               | X                                      |                | X          | X          | X         |
| Length of Stay               |  | X              |            |            |           |
| Number of outpatient therapy |  |                | X          | X          | X         |
| visits                       |  |                |            |            |           |
| Patient Satisfaction         |  | X              |            |            | X         |
| Readmissions                 |  |                | X          | X          | X         |
| Ambulation assist            | X                                      | X              | X          | X          | X         |

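### Section 7.2 sends all categorical outcomes to the order-blind Pearson chi-square; if patient satisfaction is a graded item with 3 to 5 levels, that costs about 5 to 29 points of power at 20 per group

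*Combined protocol and SAP*

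**What the plan says.** Section 7.2 gives two rules for all outcomes. For continuous measures, "Differences between means will be analyzed using Student's t-test". For the rest, "categorical variables will be tested using frequency tabulations comparing outcomes between treatments with the Pearson chi-square test". The significance level is 0.05 and sidedness is not stated. No test that uses category order is named.

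Section 1.3 lists "5) Patient satisfaction measures" among the secondary outcomes. The schedule in section 1.4 has a row for "Patient Satisfaction", marked at the day of surgery and at 12 weeks, and section 6.3 lists it again among the postoperative assessments. Nowhere do the documents name the instrument, say whether it gives a category or a score, or state how many levels it has or what difference is expected.

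The only effect size in the documents is in section 7.1 and belongs to the primary endpoint: "They found a standardized mean difference of 0.90 for quadriceps muscle strength between control and NMES intervention groups". From it the section concludes: "This study will require 20 patients per group".

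**The concern.** Satisfaction is often recorded on a graded item, for example from very dissatisfied to very satisfied. Under section 7.2 such an item would go to the Pearson chi-square. That statistic is unchanged when the categories are shuffled, and with two arms and K levels it spends K − 1 degrees of freedom on any difference in pattern. The aims in section 3 are directional (improved, fewer, decreased). A rank test puts its power into a shift in one direction. The chi-square spreads its power over all patterns, including some that favour neither arm. At about 20 patients per arm there is little power to spare, so a real benefit on a graded scale could be missed because of the choice of test.

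**Working it through.** **1. The plan's own figure.** Inputs from section 7.1: standardised difference 0.90, power 80%, alpha 0.05 (taken as two-sided).

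n per group = 2(1.960 + 0.842)² / 0.90² = 15.70 / 0.81 = 19.4, rounded up to 20.

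This reproduces the stated 20 per group. Power at 20 is 81.2% by the normal approximation and 79.2% by the exact t-test. The figure concerns quadriceps strength only. The plan states no power for any categorical outcome.

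**2. Cost of the extra degrees of freedom.** Hold the noncentrality λ fixed and compare a 1-df directional test with a (K − 1)-df test at 0.05. At λ = 6.17 the 1-df test has 70.0% power.

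| Levels K | df | Power | Loss (points) |
|---|---|---|---|
| 3 | 2 | 59.7% | 10.3 |
| 4 | 3 | 53.1% | 16.9 |
| 5 | 4 | 48.2% | 21.8 |

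**3. Simulation at 20 vs 20.** A latent normal outcome is cut into K ordered levels at the control proportions shown, and the treated arm is shifted by d SD. The uncorrected Pearson chi-square (empty levels dropped) is compared with the tie-corrected Wilcoxon rank-sum test, two-sided 0.05, 40,000 replicates per setting. The number of levels, the proportions and the shifts are all assumptions. The 0.9 is borrowed from section 7.1 for illustration.

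| Control proportions (%) | d | Chi-square | Rank-sum | Gap (points) |
|---|---|---|---|---|
| 3 levels, even | 0.5 | 21.3% | 27.4% | 6.1 |
| 3 levels, even | 0.9 | 56.4% | 66.8% | 10.3 |
| 3 levels, 20/40/40 | 0.9 | 52.4% | 64.6% | 12.2 |
| 4 levels, even | 0.5 | 19.2% | 30.0% | 10.8 |
| 4 levels, 10/20/35/35 | 0.9 | 45.6% | 67.1% | 21.6 |
| 5 levels, even | 0.5 | 16.6% | 30.4% | 13.7 |
| 5 levels, even | 0.9 | 47.2% | 72.7% | 25.5 |
| 5 levels, 5/5/15/35/40 | 0.5 | 12.1% | 27.7% | 15.6 |
| 5 levels, 5/5/15/35/40 | 0.9 | 36.7% | 65.4% | 28.7 |

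(Gaps are taken before rounding.) Over all the distributions tried, shifts of 0.5 to 0.9 SD give gaps of about 6 to 13 points for three levels and 11 to 29 for four or five. A weaker proportional-odds effect (odds ratio 2) gives 5 to 12, so the overall range is about 5 to 29.

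**4. Type I error.** The rank-sum test stays near 5% throughout (4.7 to 5.0% in these settings), so its gain is not bought with false positives. The chi-square is close to 5% with even categories. In the 5/5/15/35/40 case it is conservative, at about 3.1 to 3.4%, because 20 controls put an expected 20 × 0.05 = 1 patient in each of the two lowest levels. Compared at equal size, its power there rises from about 36% to 43%, against 65% for the rank test. So about 7 of the 29 points come from sparse cells and about 22 from ignored order.

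**5. Other contrasts.** With both NMES arms combined against control (40 vs 20) and d = 0.9, the gap is about 6 to 16 points. For an overall three-arm test (3 × K Pearson against Kruskal-Wallis, shifts of 0.5 to 1.2 SD), it is about 5 to 31 points.

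**The case against.** The strongest objection is that no ordered categorical outcome is shown to exist. Satisfaction may be a summed score or a 0 to 10 rating, which section 7.2 sends to the t-test. In the simulations the t-test had nearly the same power as the rank test. It may also be a yes/no item, for which order means nothing. This stands, and it makes the point conditional.

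A reader might infer that the plan as written loses a fixed amount of power, or that every categorical outcome suffers. The documents support neither. Readmission is binary per patient, and use of a walking aid is recorded in section 6.3 as any use, which also reads as binary. Discharge disposition has three categories with no stated order. Satisfaction appears in none of the six aims in section 3.

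The 0.9 SD shift belongs to quadriceps strength, and nothing supports one that large for satisfaction. At 0.5 SD both tests are weak (about 12 to 21% against 26 to 30%), so changing the test would not rescue the comparison. This also stands.

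Nor is the chi-square invalid here. No inflated type I error was found, and the planned frequency tables would let a reader see a pattern that favours neither arm. The issue is efficiency and fit to a directional question.

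What the objection does not remove is the rule itself. It covers every categorical variable, and with the instrument unspecified, nothing stops a graded item from going to the chi-square, or the test from being chosen after the data are seen.

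**Conclusion.** The point holds in conditional form, as a minor improvement. Section 7.2 assigns all categorical variables to a test that ignores order. The size of the loss rests on three things the documents do not give: the number of levels, their distribution and the effect. It is zero for a binary measure or a numeric score. The upper end of the range needs five levels, a large shift and, for the very largest values, a thinly filled lower end of the scale, so it should not be read as due to ignored order alone. The reach is one secondary outcome. The sample size of 20 per group reproduces and is not affected.

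**What to change.** In section 7.2:

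- Limit the Pearson chi-square to unordered or binary categories.
- Add: 'Any ordered categorical outcome, including patient satisfaction if graded, will be compared by the Wilcoxon rank-sum test for each pairwise arm contrast, with the Kruskal-Wallis test for an overall three-arm comparison.'
- State the satisfaction instrument and its levels, there or in section 1.3, so that it is settled in advance which rule applies.
- Optionally, report a proportional-odds odds ratio with its 95% confidence interval as the effect estimate, noting that it assumes a common odds ratio across the cut-points, which about 20 patients per arm can hardly check.

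The cost is a few sentences, with no new data, visits or patients. The small downside is less sensitivity to a difference in pattern without direction, which no aim asks about. If satisfaction proves to be numeric or binary, the added rule has no effect on it and does no harm.
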